8.2 Handling of Missing Data

Missing data will be imputed using the following methods for the effectiveness analyses:

- Multiple Imputation (MI): If there are any mITT participants with missing ATHS score at Month 3 on either side of temple, MI by the Fully Conditional Specification (FCS) method will be used to impute the missing data in ordinal scale by treatment group and by side of temple (left and right). [REDACTED]

- **Non-Responder Imputation (NRI):** For sensitivity analysis, the NRI method will categorize any participants with missing Month 3 ATHS scores as non-responders.
- **As Observed (AO):** The AO method will analyze the data based on the observed values without imputation for the missing values. Thus, a participant who does not have an evaluation on a scheduled visit will be excluded from the AO analysis for that visit. The AO method will be used for sensitivity analysis of primary effectiveness endpoint using the OPE population.

8.3 Primary Effectiveness Endpoint(s) and Analyses

8.3.1 Primary Effectiveness Endpoint(s)

The primary effectiveness endpoint is the ATHS responder status at Month 3 in CP based on EI's assessment. A responder is defined as a participant with at least 1-grade improvement (reduction) from baseline on the ATHS (described in Table 5) on both temples. Each side of temple will be assessed independently by the blinded EI.

Table 5. Allergan Temple Hollowing Scale

Score	Grade	Description
0	Convex	Rounded temple
1	Flat	Flat temple; temporal fusion line may be visible
2	Minimal	Shallow depression or concavity with minimal volume loss; temporal fusion line may be visible
3	Moderate	Moderate depression or concavity with moderate volume loss; moderate prominence of temporal fusion line
4	Severe	Deeply recessed, sunken appearance; marked prominence of temporal fusion line and zygomatic arch

[REDACTED]

[REDACTED]

[REDACTED]

[REDACTED]

[REDACTED]

[REDACTED]

[REDACTED]

[REDACTED]

8.3.3 Primary Effectiveness Analysis

Primary effectiveness analysis will be performed based on the mITT population. The study intervention will be considered clinically effective if both of these criteria are met:

- The ATHS responder rate for the treatment group is statistically superior to the responder rate for the control group at Month 3
- At least 60% (a point estimate of 60% or greater) of participants treated with VOLUMA XC are ATHS responders at Month 3

For the first criterion, the null and alternate hypotheses are:

$$H_0: P_v = P_c \text{ versus } H_a: P_v \neq P_c$$

where P_v and P_c denote the responder rates for the treatment group at Month 3 after the latest of randomization, initial treatment and touch-up treatment, and control group at Month 3 after randomization, respectively.

If there are no mITT participants with missing scores for the primary effectiveness endpoint, a 2-sided Fisher's exact test with 5% significance level will be used to compare responder rates between treatment and the control group. Otherwise, the methods described in Section 8.3.2 will be applied. If the 2-sided p-value is ≤ 0.05 , which implies that the responder rate between treatment and control is different, and the point estimate of the responder rate for the treatment group is greater than for the control group and is 60% or greater, then treatment will be considered clinically effective. In addition, responder rates and 95% CIs will be calculated for treatment group and control group. No hypothesis testing will be performed for the second criterion.

8.3.4 Additional Analyses of the Primary Effectiveness Endpoint(s)

If there are any mITT participants with missing scores for the primary effectiveness endpoint, then a sensitivity analysis of the primary effectiveness endpoint will be performed for the OPE population using the Fisher's exact test for group comparison.

A second sensitivity analysis of the primary effectiveness endpoint will also be performed for the mITT population with missing ATHS responder status at Month 3 imputed as non-responders.

Summary of sensitivity analyses are presented in Table 6.

Table 6. Missing Data Handling Rules for the Sensitivity Analyses of the Primary Endpoint

Endpoint	Sensitivity Analysis No.	Missing Data Handling Rule	Population	Methodology
ATHS responder status at Month 3	1	AO method	OPE	Fisher's exact test
ATHS responder status at Month 3	2	NRI method	mITT	Fisher's exact test

8.4 Secondary Effectiveness Analyses

There are 4 secondary effectiveness measures, to be recorded at the participant level rather than for each temple. The secondary effectiveness endpoints include:

- Responder status for EI assessment of GAIS (described in Table 7) in the temple area at Month 3 during CP
- Responder status for participant assessment of GAIS in the temple area at Month 3 during CP
- Change from baseline in participant responses to FACE-Q Satisfaction with Facial Appearance questionnaire, for the Rasch-transformed score (0 - 100) at Month 3 during CP

- Change from baseline in participant responses to FACE-Q Satisfaction with Temples questionnaire, for the Rasch-transformed score (0 - 100) at Month 3 during CP

A GAIS responder for EI assessment is defined as a participant who shows improvement in the overall aesthetic assessment (Improved or Much Improved on GAIS) based on EI assessment in the temple area at the Month 3 visit.

A GAIS responder for participant assessment is defined as a participant who shows improvement in the overall aesthetic assessment (Improved or Much Improved on GAIS) based on participant assessment in the temple area at the Month 3 visit.

The GAIS responder rates based on EI assessment and participant assessments at Month 3 will be analyzed by descriptive statistics. The responder rates and the corresponding exact 95% CI will be estimated for treatment group and control group. The between-group difference in the responder rate and the corresponding 95% CI will be estimated, which will be considered descriptive and will be used to support the primary endpoint. No hypothesis testing procedure is planned to compare the treatment and control groups on the GAIS responder status based on EI and participant assessments.

Table 7. Global Aesthetic Improvement Scale

Grade	Description
Much Improved	Marked improvement in appearance
Improved	Improvement in appearance, but a touch-up or retreatment is indicated
No Change	The appearance is essentially the same as the original condition
Worse	The appearance is worse than the original condition
Much Worse	The appearance is much worse than the original condition

The other secondary effectiveness measures are the participant responses on the FACE-Q questionnaires: Satisfaction with Facial Appearance and Satisfaction with Temples. The scales and scoring algorithms for FACE-Q questionnaires can be found in Appendix F.

For both FACE-Q scales, change from baseline to Month 3 on the Rasch-transformed score (0-100) of FACE-Q Satisfaction with Facial Appearance questionnaire, and change from baseline to Month 3 on participant responses on the Rasch-transformed score (0-100) of FACE-Q Satisfaction with Temples questionnaire will be tested within the treatment group with a 2-sided paired t-test at the 5% level to determine if the mean Rasch-transformed satisfaction score at Month 3 is statistically greater than that at baseline for the treatment group. The estimate, 95% CI, and p-value will be provided for the within-group change from Baseline to Month 3 for treatment group and control group.

For FACE-Q Satisfaction with Facial Appearance questionnaire and FACE-Q Satisfaction with Temples questionnaire, the responses to all the items will be summed and converted to a Rasch-transformed score that ranges from 0 to 100 (higher score indicates increased satisfaction) using the algorithm developed by the FACE-Q scale developers¹ (Appendix F-1, Appendix F-2).

For items with missing data (which includes selection of more than 1 response for an item, a response of non-applicable (N/A) or skipping a question), insert the unrounded mean of the completed items into the total sum score. The summed score including the imputation of missing items is rounded to the nearest integer and converted to the Rasch transformed score using the conversion table below. Higher scores reflect a better outcome. The converted score ranges from 0 (worst) to 100 (best). If less than 50% of the questions have been answered, then the overall score will be missing.

The secondary effectiveness endpoints will be analyzed based on mITT population based on the observed data.

■ [REDACTED]

[REDACTED]

[REDACTED]

[REDACTED]

[REDACTED]

[REDACTED]

[REDACTED]

[REDACTED]

[REDACTED]

[REDACTED]

[REDACTED]

[REDACTED]

[REDACTED]

[REDACTED]

[REDACTED]

[REDACTED]

[REDACTED]

[REDACTED]

[REDACTED]

[REDACTED]

[REDACTED]	[REDACTED]	[REDACTED]	[REDACTED]	[REDACTED]
[REDACTED]	[REDACTED]	[REDACTED]	[REDACTED]	[REDACTED]
[REDACTED]	[REDACTED]	[REDACTED]	[REDACTED]	[REDACTED]
[REDACTED]	[REDACTED]	[REDACTED]	[REDACTED]	[REDACTED]
[REDACTED]	[REDACTED]	[REDACTED]	[REDACTED]	[REDACTED]
[REDACTED]	[REDACTED]	[REDACTED]	[REDACTED]	[REDACTED]
[REDACTED]	[REDACTED]	[REDACTED]	[REDACTED]	[REDACTED]
[REDACTED]	[REDACTED]	[REDACTED]	[REDACTED]	[REDACTED]
[REDACTED]	[REDACTED]	[REDACTED]	[REDACTED]	[REDACTED]
[REDACTED]	[REDACTED]	[REDACTED]	[REDACTED]	[REDACTED]
[REDACTED]	[REDACTED]	[REDACTED]	[REDACTED]	[REDACTED]
[REDACTED]	[REDACTED]	[REDACTED]	[REDACTED]	[REDACTED]
[REDACTED]	[REDACTED]	[REDACTED]	[REDACTED]	[REDACTED]
[REDACTED]	[REDACTED]	[REDACTED]	[REDACTED]	[REDACTED]
[REDACTED]	[REDACTED]	[REDACTED]	[REDACTED]	[REDACTED]

[REDACTED]

[REDACTED]	[REDACTED]	[REDACTED]	[REDACTED]	[REDACTED]
[REDACTED]	[REDACTED]	[REDACTED]	[REDACTED]	[REDACTED]
[REDACTED]	[REDACTED]	[REDACTED]	[REDACTED]	[REDACTED]
[REDACTED]	[REDACTED]	[REDACTED]	[REDACTED]	[REDACTED]
[REDACTED]	[REDACTED]	[REDACTED]	[REDACTED]	[REDACTED]
[REDACTED]	[REDACTED]	[REDACTED]	[REDACTED]	[REDACTED]
[REDACTED]	[REDACTED]	[REDACTED]	[REDACTED]	[REDACTED]

[REDACTED]

[REDACTED]

[REDACTED]

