#### Number of Participants:

Up to 213 participants will be enrolled and screened to achieve 171 randomized (114 treatment group, 57 control group) and 135 evaluable participants (90 treatment group, 45 control group) at the Month 3 primary timepoint.

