#### 8.1.3. Secondary Effectiveness Measures

There are 4 secondary effectiveness measures, to be recorded at the participant level rather than for each temple. The secondary effectiveness measures include independent, noncollaborative assessments by both the EI and the participant of global aesthetic improvement in the temple area using the 5-point GAIS (Table 8-2).

| Table 8-2 | Global Aest       | esthetic Improvement Scale  |  |
|-----------|-------------------|---|--|
| Score     | Grade Description |   |  |
| 2         | Much Improved     | Marked improvement in appearance                                      |  |
| 1         | Improved          | Improvement in appearance, but a touch-up or retreatment is indicated |  |
| 0         | No Change         | The appearance is essentially the same as the original condition      |  |
| -1        | Worse             | The appearance is worse than the original condition                   |  |
| -2        | Much Worse        | The appearance is much worse than the original condition              |  |

Participants and EIs will assess global aesthetic improvement of the temple area by comparing to frontal and lateral view photographs taken at baseline. Participants will use a mirror to assess their current appearance at each visit. All participant-reported effectiveness outcomes at a visit will be completed before the participant sees either the TI or EI at that visit.

The other secondary effectiveness measures are the participant responses on the FACE-Q questionnaires: Satisfaction with Facial Appearance and Satisfaction with Temples. In the FACE-Q Satisfaction with Facial Appearance questionnaire the responses to the 10 items will be summed and converted to a Rasch-transformed score that ranges from 0 to 100 (higher score indicates increased satisfaction) using the algorithm developed by the FACE-Q scale developers. In the FACE-Q Satisfaction with Temples questionnaire, the final scoring and items will be determined based on the analysis of psychometric properties of the scale (as discussed in Section 4.2.4) and will be specified in the SAP.

[figure not shown]

Protocol 1878-702-008 Amendment 2

| Assessment  | Timing   | Measurement   |
|---|--|---|
| Global aesthetic
improvement of the
temple area | All in-office follow-up visits starting from Month 1                         | 5-point ordinal scale from -2 to 2 (details in Table 8-2)   |

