7.0 Demographics, Baseline Characteristics, Medical History, and Prior/Concomitant Medications

7.1 Demographics and Baseline Characteristics

Demographic parameters (age; age group; sex; race; ethnicity) will be summarized descriptively in total and by treatment group for the mITT populations. Age (years) is calculated relative to informed consent date. For summary by race, participants who reported multiple races are only included in the 'Multiple' category.

Number (%) of participants who reported multiple races will be summarized as applicable.

Baseline characteristics shown below will be summarized descriptively in total and by treatment group for the mITT populations:

- Weight (kg), height (cm), and BMI (kg/m²)
- Fitzpatrick Skin Phototype (each phototype, and by phototype groups, i.e., I and II, III and IV, V and VI)
- Exposure to sunlight (hours per day)
- Smoking history (status, tobacco product, frequency, and duration in months)
- Allergan Temple Hollowing Scale
- FACE-Q Satisfaction with Facial Appearance questionnaire, for the Rasch-transformed score
- FACE-Q Satisfaction with Temple questionnaire, for the Rasch-transformed score
- Jaw Functional Limitation Scale
- Self-perception of age

Demographic and baseline characteristics will be provided in a listing.

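### FACE-Q in SAP 8.4: add a descriptive treatment-minus-control difference beside the two within-arm tests (a cheap improvement, not an error)

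*SAP*

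**What the plan says.** SAP 12.0 sets a fixed order: the ATHS primary test, then FACE-Q Satisfaction with Facial Appearance, then FACE-Q Satisfaction with Temples, each two-sided at 5%, with overall control at 0.05.

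SAP 8.4 defines the two FACE-Q tests. Change from baseline to Month 3 "will be tested within the treatment group with a 2-sided paired t-test at the 5% level", with the purpose stated as "to determine if the mean Rasch-transformed satisfaction score at Month 3 is statistically greater than that at baseline for the treatment group". On output it says: "The estimate, 95% CI, and p-value will be provided for the within-group change from Baseline to Month 3 for treatment group and control group". On population and missing data: "The secondary effectiveness endpoints will be analyzed based on mITT population based on the observed data".

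For the two GAIS secondaries, which are not tested, the same section says: "The between-group difference in the responder rate and the corresponding 95% CI will be estimated, which will be considered descriptive".

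Controls complete both FACE-Q scales at randomization and at Month 3 (Protocol Table 1-5), and SAP 7.1 lists baseline "FACE-Q Satisfaction with Facial Appearance questionnaire, for the Rasch-transformed score" and the corresponding Temples score for summary by arm. Protocol 4.1 says the study compares treatment with no treatment. The FACE-Q endpoints themselves are worded as change from baseline in Protocol section 3 and SAP 3.2.

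**The concern.** The trial randomizes a concurrent untreated group and collects both FACE-Q scales in it, but the visible plan never contrasts the two arms on FACE-Q. A significant gatekept result would support the statement that scores rose in treated participants. It would not show that they rose more than without treatment.

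The only planned view of the controls is a second within-arm p-value, from an arm half the size of the treated one. Printed side by side, the two p-values invite a comparison they cannot support: significant in one arm and not in the other is not evidence of a difference between arms. What is at stake is the interpretation of two alpha-controlled patient-reported results. The primary decision rule is between-group and is unaffected.

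**Working it through.** **1. The plan's own figure.** In a fixed sequence with every step at 0.05, the first true null in the order is tested at 0.05, so the familywise error is at most 0.05. The stated 0.05 is reproduced for the visible sequence, where each FACE-Q null is zero change within the treated arm. The interim section is redacted and is not covered by this check.

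**2. Inputs.** Planned numbers from the protocol synopsis: "135 evaluable participants (90 treatment group, 45 control group) at the Month 3 primary timepoint". The visible documents give no FACE-Q SD, effect size or correlation. Assumed here: SD of change 15, 20 or 25 points in both arms; the same true rise in both arms (true difference zero); gate open.

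**3. Within-arm tests.** For a paired t-test with n participants the noncentrality is rise / (SD / √n). Example: rise 5, SD 20, n = 90 gives 5 / (20/√90) = 2.37, and the probability of a significant rise is 0.650. With n = 45 it is 5 / (20/√45) = 1.68, and the probability is 0.375.

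**4. The misleading pattern.** With independent arms, P(treated significant, control not) = P(treated) × [1 − P(control)]. For the example, 0.650 × (1 − 0.375) = 0.41. The equal-arm benchmark puts 90 in both arms: 0.650 × (1 − 0.650) = 0.23.

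| Rise | SD | P(treated), n = 90 | P(control), n = 45 | Pattern, 90 vs 45 | Pattern, 90 vs 90 | Added by unequal arms |
|---|---|---|---|---|---|---|
| 3 | 15 | 0.467 | 0.259 | 0.346 | 0.249 | 0.097 |
| 3 | 20 | 0.290 | 0.165 | 0.243 | 0.206 | 0.037 |
| 3 | 25 | 0.202 | 0.121 | 0.178 | 0.161 | 0.017 |
| 5 | 15 | 0.879 | 0.590 | 0.360 | 0.107 | 0.254 |
| 5 | 20 | 0.650 | 0.375 | 0.407 | 0.227 | 0.179 |
| 5 | 25 | 0.467 | 0.259 | 0.346 | 0.249 | 0.097 |

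For larger common rises at SD 20 the pattern is 0.24 at 8 points, 0.09 at 10 and 0.02 at 12. At SD 25 it is 0.38, 0.24 and 0.12. In all these settings a treatment-minus-control 95% CI lies wholly above zero in about 0.025 of trials.

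**5. Precision of a difference.** √(1/90 + 1/45) = 0.1826.
- Unadjusted: t(133) × SD × 0.1826. At SD 20, 1.978 × 20 × 0.1826 = 7.2 points (5.4 at SD 15, 9.0 at SD 25).
- ANCOVA: residual SD = SD of change × √((1 + ρ)/2), assuming equal baseline and Month 3 variances, with df 132. At SD 20 and ρ = 0.5, 1.978 × 20 × 0.866 × 0.1826 = 6.3 points (4.7 at SD 15, 7.8 at SD 25). At SD 20 it is 5.8 for ρ = 0.3 and 6.7 for ρ = 0.7.
- The two estimates differ by (1 − ρ) × the baseline imbalance. With SD of change 20 and ρ = 0.5, the baseline SD is 20/√(2 × 0.5) = 20, and the 95% range of that gap is ±1.96 × 0.5 × 20 × 0.1826 = ±3.6 points.

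**6. Month 3 clock.** Controls: day 90 ± 7 from randomization, so 83 to 97 (Protocol Table 1-5). Treated without touch-up: 83 to 97 from initial treatment. With touch-up at day 30 to 40 (Tables 1-2 and 1-3): 30 + 83 = 113 to 40 + 97 = 137.

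**The case against.** The strongest case against is that nothing here is wrong. The SAP states its within-arm hypothesis openly, the error control is valid for it, and the protocol and SAP already word the endpoint as change from baseline. All of that stands. A reader might infer that the gatekeeping fails, or that the plan means to claim FACE-Q superiority over control. The documents support neither: no visible passage makes a between-group FACE-Q claim.

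Much of the information is also already planned. Subtracting the two reported mean changes gives an unbiased unadjusted difference, and combining the within-arm half-widths at SD 20 gives √(4.2² + 6.0²) = 7.3 points, against 7.2 computed directly. Under an equal-variance assumption a reader could even approximate the baseline adjustment from reported SDs. So ANCOVA gains about one point of half-width, plus protection against baseline imbalance. What remains is that the result should be planned and printed, not left to the reader.

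It is also tempting to say that the 'treated significant, control not' pattern comes from arm size alone. The 90-versus-90 column shows otherwise: at 3 points most of it is ordinary chance.

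GAIS is an imperfect parallel. It has no baseline score, because "Participants and EIs will assess global aesthetic improvement of the temple area by comparing to frontal and lateral view photographs taken at baseline", and it carries no planned test. It is a precedent for presenting a difference, not for gatekeeping one.

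Finally, SAP 8.5 is redacted and the protocol's statistical section is not in the text supplied, so a descriptive FACE-Q contrast may already exist. The point is therefore limited to the visible text.

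**Conclusion.** This holds as a cheap improvement, not as an error in the plan. In the visible SAP 8.4 text the controls' FACE-Q data are reported but never contrasted with the treated arm.

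With an equal true rise of 3 or 5 points in both arms and SD 15 to 25, the two planned p-values would show 'treated significant, control not' with probability 0.18 to 0.41. Of this, 0.11 to 0.25 would occur even with 90 per arm, and the unequal arms add 0.02 to 0.25. The pattern becomes rare once the common rise is large relative to the SD. All of these figures rest on assumed SDs and on an assumed equal rise in untreated participants; the documents give a basis for neither. The primary conclusion and the familywise error rate do not change.

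**What to change.** Keep the gatekeeping sequence as it is. In SAP 8.4 add, for each FACE-Q scale:
- The treatment-minus-control difference in Month 3 Rasch-transformed score with its 95% CI, from an ANCOVA on treatment group and baseline score (mITT, as randomized, observed data), labelled descriptive and outside the sequence.
- A statement that the two within-arm p-values are not used to compare arms.
- A note beside the result that participants are unblinded self-raters, so expectation bias remains, and that Month 3 runs from randomization in controls but from the last treatment in the treated arm. SAP 8.3.3 already accepts the same clocks for the primary endpoint.

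Date the change relative to any review of by-arm interim data, since the SAP 13.0 version history refers to an interim efficacy analysis. If redacted 8.5 already has this difference, only a cross-reference is needed.

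The cost is one short paragraph and one table per scale, with no new data, visits or alpha. The downside is a wide interval (half-width about 6.3 points at SD 20 and correlation 0.5, both assumed), which may include zero even when the paired test is significant. Gatekeeping a between-arm test instead is not proposed. At SD 20 it would raise the effect detectable with 80% power from 6.0 points to between 8.3 and 10.3, and a failed Facial Appearance test would block Temples.

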#### **Intervention Groups and Study Duration:**

• Participants will be randomized on study intervention day in a 2:1 ratio of treatment group to control group. Screening period is up to 30 days for all participants.

Protocol 1878-702-008 Amendment 2

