8.0 Effectiveness Analyses

8.1 General Considerations

- This section applies to both effectiveness and safety analyses when applicable.
- To account for different timing of VOLUMA XC treatment and comparable time frames of data collection and to enhance interpretability of effectiveness and safety analyses, the statistical analyses will be performed by the study periods defined in Table 2.
- For CP, effectiveness analyses and baseline characteristics will be performed on the mITT population using the as-randomized assignment.

- For TP, effectiveness and safety summaries will be performed on the VT population, using as-treated grouping.
- For MP, effectiveness and safety summaries will be performed on the VMT population.
- Study day refers to Day 1 regardless of study period (e.g., CP, TP, MT).
- The baseline for effectiveness and safety parameters will be the last non-missing assessment prior to or on Day 1, i.e., the latter of randomization or initial injection in Control Period. Day 1 is defined as the day on which the study intervention (VOLUMA XC or no-treatment) is first received.
- The change from baseline values will be computed as the postbaseline value minus the baseline values.
- For vision assessments, baseline will refer to the most-recent measurement just prior to the most-recent treatment.
- Continuous variables will be summarized by number of participants with observed values (n), mean, standard deviation (SD), median, 1st and 3rd quartiles (Q1, Q3), minimum (min), and maximum (max). Categorical variables will be summarized by the number of participants with observed values or events (n) and the percentage of participants with observed values or events.
- All statistical hypothesis tests will be performed at the 2-sided, 5% significance level, unless stated otherwise.
- All CIs will be 2-sided 95% CIs, unless stated otherwise.
- All statistical analyses will be performed using SAS Version 9.4 or subsequent.

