12.0 Overall Type-I Error Control

All statistical tests will be 2-sided hypothesis tests performed at the 5% level of significance for main effects. All CIs will be 2-sided 95% CIs, unless stated otherwise. A gatekeeping procedure will be used for hypothesis testing of the primary endpoint (ATHS responder) and 2 of the secondary endpoints (FACE-Q Satisfaction with Facial Appearance and FACE-Q Satisfaction with Temples) following a predefined sequence to control the overall Type I error rate at the 0.05 level. The primary hypothesis must be rejected in order to test the FACE-Q Satisfaction with Facial Appearance. Additionally, statistical significance must be established for FACE-Q Satisfaction with Facial Appearance in order to assess the hypothesis for FACE-Q Satisfaction with Temples.

For the secondary effectiveness endpoints of GAIS responder status at Month 3 as assessed by the EI and as assessed by the participant, the 95% CI will be provided for the proportion of responders within each treatment group, where applicable. No multiplicity

adjustments will be made for the 2 GAIS responder rates since these endpoints and associated statistics are intended to be descriptive rather than inferential.

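### Both gatekept FACE-Q changes and both GAIS responder rates use observed Month 3 data only, with no readable provision for a missed visit, although Month 1 values are collected in both arms

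*SAP*

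**What the plan says.** SAP 8.4 sets the rule for all four secondary endpoints (GAIS by the evaluating investigator (EI), GAIS by the participant, FACE-Q Facial Appearance, FACE-Q Temples): "The secondary effectiveness endpoints will be analyzed based on mITT population based on the observed data". SAP 8.2 says what an as-observed analysis does: "a participant who does not have an evaluation on a scheduled visit will be excluded from the AO analysis for that visit".

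The other two methods readable in SAP 8.2, multiple imputation and non-responder imputation, are written for the Month 3 ATHS score. SAP Table 6 lists sensitivity analyses for the primary endpoint only. SAP 8.4 and Appendix F do fill in skipped FACE-Q items, but only within a questionnaire that was returned.

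SAP 12.0 gives two of the four endpoints confirmatory status: "A gatekeeping procedure will be used for hypothesis testing of the primary endpoint (ATHS responder) and 2 of the secondary endpoints". Those two are the FACE-Q scales, each tested by a paired t-test within the treatment group. The GAIS rates are descriptive, and SAP 8.4 uses the between-group GAIS difference as support for the primary endpoint.

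The protocol synopsis plans: "Up to 213 participants will be enrolled and screened to achieve 171 randomized (114 treatment group, 57 control group) and 135 evaluable participants", split 90 and 45 by arm. Protocol Tables 1-3 and 1-5 schedule FACE-Q and both GAIS ratings at Month 1 as well as Month 3, in both arms.

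**The concern.** The population is labelled mITT, but anyone without a Month 3 value drops out of the secondary estimates, so in effect these are completer analyses. Within one gatekept family, the first test is imputed and probed by two further analyses, while the second and third are neither.

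FACE-Q and participant GAIS are self-reported by participants who know their treatment, so loss related to satisfaction is plausible. EI GAIS is rated by a blinded evaluator, and that argument does not apply to it in the same way, but it too is missing when a participant leaves. Because the FACE-Q tests are within-group, no control comparison can offset selective loss in the treatment arm. At stake are the size and confidence interval of the FACE-Q changes and the denominators of the GAIS rates. Month 1 data that could reduce the problem are already collected.

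**Working it through.** **1. Planned loss (protocol synopsis, number of participants).**
- Total: (171 − 135)/171 = 36/171 = 21.05%.
- Treatment: (114 − 90)/114 = 24/114 = 21.05%.
- Control: (57 − 45)/57 = 12/57 = 21.05%.
- Reproduction of the plan's figures: n/(1 − 0.21), rounded up, gives 135 → 171, 90 → 114 and 45 → 57, all exact. A 20% allowance gives 169, 113 and 57, which is close but not exact.

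No dropout rate appears in the readable text, and the text of SAP 2.4 is not available. The 21% is therefore an inferred allowance for the primary timepoint, borrowed here for the secondary endpoints.

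**2. Bias in the FACE-Q estimate.** The documents give no SD, effect or correlation. Assumptions: true mean change 18, SD 20, Month 1 to Month 3 correlation 0.7, loss of 24/114 depending on the Month 1 score through a logistic model. The bias in the observed-case mean is SD × correlation × (mean standardized Month 1 score among those retained).

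| Odds of leaving per SD poorer Month 1 score | Mean Month 1 z, retained | Bias = 20 × 0.7 × z | Observed-case mean |
|---|---|---|---|
| 1.0 | 0 | 0 | 18.0 |
| 1.4 | 0.069 | +1.0 | 19.0 |
| 2 | 0.136 | +1.9 | 19.9 |
| 3 | 0.194 | +2.7 | 20.7 |

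This is 5% to 15% of the assumed change. Varying the correlation from 0.5 to 0.8 and the log-odds slope from 0.5 to 1.0 gives a bias of 0.05 to 0.14 SD.

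**3. Precision if loss is unrelated to outcome.**
- Observed cases: SE = 20/√90 = 2.11.
- Using Month 1: SE = 20 × √[(1 − 0.7²)/90 + 0.7²/114] = 2.00.

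**4. Does the gatekept decision change?** Let d be the observed mean change divided by the SD. The observed-case t is d√90. If the 24 missing participants had mean change zero with the same SD, then t = (90d/114) × √114 / √[1 + (90 × 24/114²)d²].

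| d | t, observed cases | t, missing at mean zero |
|---|---|---|
| 0.25 | 2.37 | 2.10 |
| 0.5 | 4.74 | 4.13 |
| 0.9 (18/20) | 8.54 | 7.12 |

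The critical value on 113 degrees of freedom is 1.98, so significance survives in every row.

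**5. GAIS range.** For an assumed observed rate p in the treatment arm, the rate over all 114 lies between 90p/114 and (90p + 24)/114.
- 60%: 54/114 = 47.4% to 78/114 = 68.4%.
- 80%: 72/114 = 63.2% to 96/114 = 84.2%.
- 90%: 81/114 = 71.1% to 105/114 = 92.1%.
- Control with 0/45 observed: 0% to 12/57 = 21.1%.

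For the difference, take 80% against 0% observed. Counting missing as non-response in both arms gives 63.2 points. Counting missing control participants as responders instead gives 63.2 − 21.1 = 42.1 points. Missing-as-non-response is therefore the low end for each arm's rate but not for the difference.

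**The case against.** - **The decision would not change.** This stands. A reader might infer that the alpha-controlled claim is in danger; step 4 does not support that. The point concerns the estimate and interval.
- **The plan forecasts 21% missing FACE-Q and GAIS.** A reader might infer this, but the documents do not say it. The counts concern evaluability at the primary timepoint, and actual loss could be smaller.
- **Nothing planned would reveal the loss.** This too would be an overstatement. SAP 5.2 tabulates discontinuations and reasons during the control period, and ATHS, due at the same visit, is analysed three ways. These show how many left and why, but they do not correct or bound the FACE-Q and GAIS estimates. SAP 8.5, 8.6 and the interim section are redacted, so an additional analysis there cannot be excluded; the observed-data sentence itself is explicit and readable.
- **The bias figures are assumed.** This stands. Nothing in the documents shows that dissatisfied participants leave. In step 2 loss depends on Month 1 alone and everyone has a Month 1 value, so imputing from Month 1 recovers 18.0 by construction. Treatment-arm Month 1 falls 30 days after the last treatment, so anyone lost earlier has only a baseline FACE-Q and no GAIS.
- **The low GAIS figures are worst cases.** This stands, which is why step 5 shows both ends. The supporting role in SAP 8.4 belongs to the descriptive difference, not to a single-arm rate.

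**Conclusion.** The point holds as a worthwhile, inexpensive improvement. All four secondary endpoints, including two of the three gatekept tests, exclude anyone without a Month 3 value, and the readable plan has no missing-visit analysis for them. With loss near the derived 21% allowance and dependent on Month 1 satisfaction, the FACE-Q mean would be too high by about 1 to 3 points on a 0 to 100 scale. An assumed 80% GAIS rate would leave a range 21 points wide. The FACE-Q sizes rest on the assumed mean, SD, correlation and dropout strength; the GAIS range rests only on the assumed observed rate and the planned counts. With little missing data, or loss unrelated to outcome, the observed-case and imputed results would nearly coincide.

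**What to change.** In SAP 8.4, replace the observed-data sentence for FACE-Q with one prespecified method for the gatekept tests: multiple imputation by treatment group in all mITT participants, using baseline and Month 1 FACE-Q (baseline only for those lost before Month 1), with a test of the pooled mean within-group change. Apply the existing item-level rule first. Keep the observed-case paired t-test as a sensitivity analysis.

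For GAIS, keep the observed rates and add an mITT version counting missing as non-response, for both arms and for the between-group difference.

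The cost is SAP wording and modest programming, with no new data. The secondary figures may become less favourable. The change does not fully correct for losses before Month 1, or for losses that depend on the unseen Month 3 value.
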